7.5. Central review of imaging data

Progression status will be assessed by a blinded central independent review at the neuroradiological reference center.

All imaging data must be uploaded into the provided eCRF system within 7 days.

7.6. Methodological continuity

All tests and examinations will be carried out under identical conditions, at the time points specified in the Examination Schedule.

8. Assessment of Safety

8.1. Assessment and reporting of adverse events

8.1.1. Terminology

Adverse Events are diseases, signs or symptoms, that occur or worsen after initiation of study treatment.

8.1.2. Assessment criteria

The severity of adverse events will be graded as per the assessment criteria of NCI CTCAE Version 5.0:

- Grade 1 (mild)
- Grade 2 (moderate)
- Grade 3 (severe)
- Grade 4 (life-threatening)
- Grade 5 (fatal)

If the severity of an AE should change during the observation period, the highest severity of the AE will be recorded.

The investigator must assess the causality of each adverse event. Causal relationships can be defined as follows:

- Causal relationship with the tumor
- Causal relationship with radiation treatment
- Causal relationship with other treatment measures
- Other
- Unknown

8.1.3. Documentation of adverse events

All Adverse Events must be documented according to NCI CTCAE v5.0 with its highest NCI CTCAE severity grade in the appropriate toxicity section of the eCRF, together with a short judgment on causality.

The following information must be recorded for each adverse event:

- Description of the Adverse Event according to CTCAE v5.0
- Date of onset and date of resolution
- The grade as assessed by the investigator according to the definitions in NCI-CTCAE 5.0
- Assessment of causality
- Outcome
- Treatment or action taken
- Led to study discontinuation: Yes/No

It is the responsibility of the investigator that any necessary additional therapeutic measures and follow-up procedures are performed. All adverse events must be monitored until their resolution or stabilization.

9. Statistical methods and sample size

9.1. Research question and hypothesis

The primary research question to be answered in this randomized controlled trial is whether FSRT (experimental arm) achieves significantly better local control than the "gold standard", single-fraction SRS (control group) in patients with large brain metastases. The time to local progression (TTLP) of the irradiated lesions will be used as the primary endpoint for efficacy. TTLP is defined as the time from randomization until the detection of progression as per the *RANO-BM* criteria (cf. Section 8.1 – 8.3). Patients will be censored if they have no signs of local progression at the time of last tumor monitoring during follow-up or at the onset of one of the following competing risk events not associated with, or preceded by local progression: death, lost to follow up, unauthorized non-protocol treatment of the target lesions. The following hypotheses will be tested:

H0: HR (FSRT vs. SRS as standard) ≥ 0

H1: HR (FSRT vs. SRS as standard) < 0

HR = Hazard ratio

One-sided testing of the primary endpoint will be performed based on the formulated hypotheses.

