4.4.5. Dose prescription and dose specification

Prescribing, recording and reporting should be performed according to the ICRU Report 91 guidelines. (ICRU 2017)

In the control arm, brain metastases will be treated by single-fraction SRS according to RTOG 9005 guidelines. These patients will receive a single fraction of either 24 Gy (diameter: ≥ 1 cm and < 2 cm), 18 Gy (diameter: ≥ 2 cm and < 3 cm) or 15 Gy (diameter: ≥ 3 cm and ≤ 4 cm), depending on the largest diameter of the metastasis to be irradiated.

Metastases in the experimental arm will be treated with hypofractionated stereotactic radiotherapy (FSRT). Patients in the FSRT group will receive a total dose of 48 Gy in 12 daily fractions of 4 Gy each (with weekend breaks).

The target-encompassing isodose should be 50-80% in the control arm (single-fraction SRS) and 80% in the experimental arm (FSRT).

The dose specification will be set to the target-encompassing isodose normalized to the maximum dose ($D_{max} = 100\%$). The dose calculation grid size has to be 2 mm or finer according to ICRU 91 (ICRU 2017). Advanced type-b model-based dose calculation algorithms like Monte Carlo techniques and deterministic solvers (e.g. Acuros AXB, Varian) must be used (ICRU 2017).

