5.1.3. Final examination

6 weeks after the last radiation treatment. A deviation from the exactly specified date of up to ± 1 week is acceptable. If one follow-up examination is delayed, the date of the next follow-up examination should not be postponed but should be conducted at the specific prespecified date following radiotherapy.

1. Magnetic resonance imaging (MRI) of the brain

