**2. Performance status assessment**

ECOG / KPS

3. Assessment of Adverse Events

NCI CTCAE v5.0

4. Assessment of Quality of Life

EORTC QLQ-C30

EORTC QLQ-BN20

5. Documentation of glucocorticoid dose**6. Documentation of systemic treatment****5.1.4. Follow-up examinations**

3 months after radiotherapy, then every 3 months up to a period of 2 years after the last radiation treatment. A deviation from the exactly specified date of up to ± 2 week is acceptable. If one follow-up examination is delayed, the date of the next follow-up examination should not be postponed but should be conducted at the specific prespecified date following radiotherapy.

1. Magnetic resonance imaging (MRI) of the brain**2. Performance status assessment**

ECOG / KPS

3. Assessment of Adverse Events

NCI CTCAE v5.0

4. Assessment of Quality of Life

EORTC QLQ-C30

EORTC QLQ-BN20

5. Documentation of glucocorticoid dose**6. Documentation of systemic treatment**

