7.3. Methods and criteria for efficacy evaluation

Imaging studies for the determination of tumor control will be performed as specified in the Examination Schedule. In addition to MRI-based radiotherapy planning, MRI studies will first be performed 6 weeks after the last RT treatment and then every 3 months thereafter in accordance with the general guidelines for routine diagnostic imaging in the absence of progression or clinical symptoms. Imaging intervals may need to be shortened, if an increase in size has occurred (see below). If the patient develops any signs or symptoms suspicious of progression or radionecrosis an MRI should be performed promptly.

Primary endpoint: Local control and radionecrosis according to unidimensional criteria

Local progression is defined according to the *RANO-BM* criteria by an increase of at least 20% in the longest diameter of the metastasis relative to nadir or baseline. In addition to the relative increase of 20% the lesion must increase by an absolute value of 5 mm or more.

If a metastasis has fulfilled these criteria for progression but shows spontaneous regression during subsequent imaging follow-up back to baseline or nadir diameter or a relative decrease in the longest diameter of at least 30% compared to the maximum size during enlargement, this will be scored as radionecrosis instead of progression (see 8.3). A decrease in diameter of at least 30% corresponds to the *RANO-BM* criteria for partial response in brain metastases. The date of the event will be backdated to the first imaging showing an increase in largest diameter of at least 20% and 5 mm or more. Similarly, if a metastasis shows regression according to the above-mentioned criteria after initiation of treatment for suspected radionecrosis (e.g. corticosteroids, Bevacizumab), this will also be scored as radionecrosis.

It is possible for a lesion to experience radionecrosis first, e.g. a transient increase in diameter followed by a spontaneous regression according to the above-mentioned criteria, and true progression, e.g. an increase in diameter without spontaneous regression, during subsequent follow-up.

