9.2. Sample size calculation

On the basis of available retrospective and dose-response relationship data, it is expected that SRS will result in a 12-month local tumor control rate of approximately 65% and that FSRT can increase this rate to about 80% (cf. Section 1.4). This difference is considered to be clinically significant. A sample size of N=191 evaluable cases each in the experimental and control arm, respectively, corresponding to a total of 382 patients, is required to detect a significant difference i.e. an increase in TTLP at least this large at 12-month follow-up in a randomized comparison. The number of TTLP events to be observed is 82. This calculation is based on the following framework conditions:

- The risk of making a false claim of superiority of FSRT which actually does not exist is 2.5% (α error, one-sided).
- The success rate for identifying superiority of FSRT over the control arm which actually exists is 80% (power, $1-\beta$ error).
- Assuming an exponential decline of TTLP curves
- As this is a basically palliative setting with disseminated disease, it must be considered that about half of the patients will be dead at 12-month follow-up. Consequently, a considerable proportion of patients

will have a truncated follow-up in which no event related to the primary endpoint occurs. The extent of this quasi-drop-out process is estimated to be $\leq 50\%$ and is also assumed to be exponentially distributed over the 12 months.

- Duration of follow-up for all patients: at least 12 months or until the incidence of local progression.

Note: Due to patient entry kinetics during the planned recruitment, and due to the intended follow-up period of up to 24 months for each patient (cf. section 5.1.4), the follow-up periods for a considerably number of patients, mainly those randomized early, may be significantly longer than 12 months by the end of the study. This should result in an increase in the expected number of observed events, leading to a further increase in power of the study. Since this effect is difficult to quantify (especially due to death as a competing risk event), it is not taken into account in sample size calculation, to be on the safe side. Therefore, the recruitment period is not included among the parameters provided above.

Sample size estimates were calculated based on the method of LACHIN and FOULKES (Lachin et al. 1986), applying the software NSURV (idv, Gauting, Germany).

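### TTLP is counted from randomization but scheduled MRIs from the end of radiotherapy, about two weeks later in the FSRT arm, so the one-sided 2.5% error is exceeded in favour of FSRT

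*Protocol*

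**What the plan says.** - **Endpoint clock (section 9.1).** "TTLP is defined as the time from randomization until the detection of progression as per the" RANO-BM criteria. Patients without progression are censored at their last tumor assessment, or at death, loss to follow-up or non-protocol treatment of the target lesions.
- **Scan clock.** The first follow-up MRI is due "6 weeks after the last radiation treatment" (section 5.1.3). Later ones are due "3 months after radiotherapy, then every 3 months up to a period of 2 years after the last radiation treatment" (section 5.1.4). Section 7.3 also counts from the last treatment: "MRI studies will first be performed 6 weeks after the last RT treatment and then every 3 months thereafter". The examination schedule in the synopsis does the same.
- **Treatment length (section 4.4.5).** Control arm: "These patients will receive a single fraction of either 24 Gy", 18 Gy or 15 Gy by diameter. Experimental arm: "48 Gy in 12 daily fractions of 4 Gy each (with weekend breaks").
- **Test.** Section 9.2: "The risk of making a false claim of superiority of FSRT which actually does not exist is 2.5"%, one-sided. Section 9.4 makes a stratified log-rank test the main analysis.
- **Event date.** Sections 7.3 and 7.4 backdate an event to the first imaging that shows the qualifying increase. Section 7.3 also asks for a prompt MRI when symptoms arouse suspicion.

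**The concern.** Two clocks are in use, and they differ by arm. Progression that has occurred but has not been imaged does not count as an event. On the day of each scheduled SRS scan, the FSRT patients who have progressed since their previous scan still sit in the risk set as event-free, because their matching scan comes about two weeks later. A log-rank test on detection dates reads this as a lower hazard under FSRT.

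At stake is the trial's only confirmatory error rate. The distortion works in the direction of the hypothesis under test, and nothing the protocol states removes it. Backdating still ends on an MRI date from the shifted calendar. Central review protects the reading of a scan, not its date. The visit windows (±1 and ±2 weeks) are the same in both arms. The sensitivity analyses in section 9.4 (generalized Wilcoxon, cumulative incidence) use the same event dates.

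**Working it through.** **1. The plan's own sample size.** Inputs from section 9.2: 12-month control 65% and 80%, 50% exponential loss by 12 months, one-sided 2.5%, power 80%.
- Yearly hazards: λ₁ = -ln 0.65 = 0.4308, λ₂ = -ln 0.80 = 0.2231 (HR 0.52), loss η = ln 2 = 0.6931.
- Event probability by 12 months: P(λ) = λ/(λ+η) × (1 - e^-(λ+η)), giving 0.2587 for SRS, 0.1461 for FSRT and 0.2050 at the mean hazard 0.3270.
- With φ(λ) = λ²/P(λ), Lachin-Foulkes gives N = [1.96√(4 × 0.5216) + 0.8416√(2 × (0.7173 + 0.3408))]² / 0.2076² = 381.5, i.e. 191 per arm.

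The 191 per arm is reproduced, so the same exponential model can be used for the check.

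**2. The offset.** Twelve weekday fractions starting on a Monday end on the Tuesday two weeks later: 15 days. A Friday start ends on a Monday: 17 days. A single fraction: 0 days. The wait from randomization to first treatment is not given and is assumed equal in both arms.

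**3. Expected log-rank contribution by hand.** No true difference, 65% control in both arms, 191 per arm, scans at 6 weeks and at 3, 6, ... 24 months, risk from randomization, FSRT scans 15 days (0.041 years) later. The 6-month pair:
- SRS scan, 0.50 years. At risk: SRS 191 × 0.5^0.50 × 0.65^0.25 = 121.3; FSRT 191 × 0.5^0.50 × 0.65^0.291 = 119.1. SRS events: 135.1 × (0.8979 - 0.8062) = 12.4. Observed minus expected for FSRT: -12.4 × 119.1/240.4 = -6.14.
- FSRT scan, 0.541 years. At risk: SRS 105.8, FSRT 115.8. FSRT events: 11.8. Observed minus expected: 11.8 × 105.8/221.6 = +5.65.
- Net: -0.49.

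The nine pairs give +1.17, -0.24, -0.49, -0.37, -0.28, -0.21, -0.16, -0.12 and -1.14, in total about -1.83. The first is positive because the longer first FSRT interval catches more events. The last is large because the final FSRT scan comes after SRS follow-up has ended. With about 121 events the standard deviation is about 5.5, so mean z = -1.83/5.5 = -0.33, and the rejection rate is Φ(-1.96 + 0.33) ≈ 5.2%.

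If risk starts at the end of radiotherapy, the first pair loses its compensation. The simulated mean z is then -0.61, so Φ(-1.96 + 0.61) ≈ 8.9%.

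**4. Simulation.** Same model with the protocol's visit windows, 15-day shift, 10,000 trials per row (simulation error 0.2-0.3 points). One-sided rejection in favour of FSRT:

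| Null scenario | Risk from randomization | Risk from end of RT |
|---|---|---|
| 65% control, 24-month follow-up | 5.1% | 9.0% |
| 72.5% control | 4.6% | 7.6% |
| 80% control | 4.7% | 6.5% |
| 65%, 20% of progressions found by symptom-driven MRI | 4.6% | 7.4% |
| 65%, 40% found by symptom-driven MRI | 3.6% | 6.5% |
| 65%, analysed at the 82nd event | 3.6% | 6.6% |
| 65%, calendar cut-off at 4 years | 4.5% | 7.6% |

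A mix of 15- and 17-day courses gives 5.5% with risk from randomization. Without the shift the test is nominal (2.4%). The spurious HR is about 0.93.

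**5. The remedy.** On the same shifted data an interval-censored exponential model rejected 2.1-2.7% of the time with risk from randomization, but 4.3-4.7% with risk from the end of radiotherapy.

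**The case against.** The strongest reply is that the size depends on matters the protocol leaves open. Much of that stands.

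- Section 7.3 requires prompt imaging on suspicion, so not all progression waits for a scheduled scan. The share found this way is unknown. At 40% the error is 3.6%; at an assumed 30% combined with analysis at 82 events it is 3.3%. Prompt scans dilute the bias but do not remove it.
- The wait to first treatment is not fixed. If SRS began 5 days later than FSRT, the error would be about 4.4%.
- A reader might infer that every FSRT event is recorded 15 days late. That does not follow: once the grid is shifted, the average lag from true progression to the next scan is similar in the later intervals. The bias comes from the order of the paired scans and from the end of follow-up.
- A reader might want a larger figure because one progressing lesion makes a patient-level event. At 58% one-year failure the error reached 5.7-8.8%, but that rate is assumed; section 9.2 plans with 35% and 20%.
- The scan rule is open and worded alike for both arms, and a spurious HR of 0.93 is small beside the design HR of 0.52. Only a borderline result would change.
- An unseen SAP may add an interval-censored sensitivity analysis. It would not displace the main test, clocks and error level that the protocol itself fixes.

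**Conclusion.** The point holds. The stated one-sided 2.5% is exceeded in every shifted scenario examined, always in favour of FSRT: about 3.5-5.5% if risk runs from randomization, about 6.5-9% if it starts at the end of radiotherapy. These figures assume equal waits to treatment, exponential progression and death as in section 9.2, and the stated shares of symptom-driven scans. Neither a single narrow figure nor the claim that progression is seen only at scheduled MRIs is supported.

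It would also be too strong to infer that interval censoring cures the problem. It removes the scan-timing bias. If risk starts at the end of radiotherapy, part of the offset lies in the time origin and remains. Only an exponential version was tested, on exponential data.

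**What to change.** Before any efficacy analysis:
1. Amend section 9.4, and the SAP with it, so that the primary TTLP analysis is interval-censored. The event lies between the last MRI without and the first MRI with the qualifying increase, on actual scan dates, stratified by the two randomization factors. A generalized log-rank test or an interval-censored proportional hazards model would serve.
2. Keep the planned stratified log-rank test as a sensitivity analysis.
3. Add a sensitivity analysis with the time origin at the end of radiotherapy, and state that interval censoring alone leaves part of the inflation if risk starts there. With the log-rank test this origin gave 2.5% in that case, but over-corrected to 1.3% when risk ran from randomization, so the two origins should be read together. Patients who do not complete radiotherapy need a defined origin date.
4. Time any MRIs not yet scheduled from randomization, equally in both arms. With aligned scans the error was 2.4%.

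The cost is less familiar software (R is already listed in section 9.4) and a small change of wording. No extra patients or scans are needed. Power under the interval-censored test was not recomputed and should be confirmed.

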9.2. Sample size calculation

On the basis of available retrospective and dose-response relationship data, it is expected that SRS will result in a 12-month local tumor control rate of approximately 65% and that FSRT can increase this rate to about 80% (cf. Section 1.4). This difference is considered to be clinically significant. A sample size of N=191 evaluable cases each in the experimental and control arm, respectively, corresponding to a total of 382 patients, is required to detect a significant difference i.e. an increase in TTLP at least this large at 12-month follow-up in a randomized comparison. The number of TTLP events to be observed is 82. This calculation is based on the following framework conditions:

- The risk of making a false claim of superiority of FSRT which actually does not exist is 2.5% (α error, one-sided).
- The success rate for identifying superiority of FSRT over the control arm which actually exists is 80% (power, $1-\beta$ error).
- Assuming an exponential decline of TTLP curves
- As this is a basically palliative setting with disseminated disease, it must be considered that about half of the patients will be dead at 12-month follow-up. Consequently, a considerable proportion of patients

will have a truncated follow-up in which no event related to the primary endpoint occurs. The extent of this quasi-drop-out process is estimated to be $\leq 50\%$ and is also assumed to be exponentially distributed over the 12 months.

- Duration of follow-up for all patients: at least 12 months or until the incidence of local progression.

Note: Due to patient entry kinetics during the planned recruitment, and due to the intended follow-up period of up to 24 months for each patient (cf. section 5.1.4), the follow-up periods for a considerably number of patients, mainly those randomized early, may be significantly longer than 12 months by the end of the study. This should result in an increase in the expected number of observed events, leading to a further increase in power of the study. Since this effect is difficult to quantify (especially due to death as a competing risk event), it is not taken into account in sample size calculation, to be on the safe side. Therefore, the recruitment period is not included among the parameters provided above.

Sample size estimates were calculated based on the method of LACHIN and FOULKES (Lachin et al. 1986), applying the software NSURV (idv, Gauting, Germany).

9.3. Patient evaluation categories

If a major eligibility violation occurs, the affected subject will be excluded from the statistical analysis and classified as "ineligible" (in accordance with the ICH E9 statistical principles for clinical trials). Only case reports will be presented for these patients.

All other patients will be included in an intention-to-treat analysis of the primary endpoint. A per-protocol analysis including only those patients who fully completed radiotherapy according to protocol will also be performed, as a sensitivity analysis.

All patients who received at least one dose of radiation treatment according to protocol will be included in the toxicity analysis.

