2.1. Type of study

Investigator-initiated, multicenter, open, randomized controlled phase III superiority trial.

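### The primary analysis called intention-to-treat drops randomized patients with a major eligibility violation, in an open trial with no all-randomized analysis named

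*Protocol*

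**What the plan says.** Protocol Section 9.3 sets out three steps.

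- Exclusion: "If a major eligibility violation occurs, the affected subject will be excluded from the statistical analysis and classified as" ineligible. The sentence refers to ICH E9, and these patients are presented only as case reports.
- Primary set: "All other patients will be included in an intention-to-treat analysis of the primary endpoint".
- Sensitivity set: a per-protocol analysis of patients who completed radiotherapy according to protocol.

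The same section puts every patient with at least one protocol dose of radiation into the toxicity analysis.

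Section 2.1 describes the design: "Investigator-initiated, multicenter, open, randomized controlled phase III superiority trial". Section 7.5 provides blinded central review of progression status. Section 9.1 counts time to local progression (TTLP) from randomization, and Section 9.4 makes a stratified log-rank test the main analysis, at one-sided 0.025. Section 9.2 gives the size: "A sample size of N=191 evaluable cases each in the experimental and control arm, respectively, corresponding to a total of 382 patients". The synopsis plans the same 382.

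**The concern.** The exclusion acts on randomized patients, since someone never randomized would not need removing from the analysis. Intention-to-treat means keeping patients in the arm to which they were allocated, whatever is learned later. A set defined as everyone except those judged ineligible does not do that, so the name is wrong and the protection of randomization is partly given up in the confirmatory test.

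In an open trial, whoever judges eligibility after randomization may know the arm and possibly the outcome. Blinded reading of progression does not reach that decision. Some entry criteria call for judgement, such as life expectancy in Section 3.1 and relevant overlap with prior radiation fields in Section 3.2. The protocol does not say whether a breach of these would count as major.

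The only other efficacy population named in Section 9.3 is the per-protocol set, which is narrower still. If exclusions shifted the result, no planned analysis would show it.

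**Working it through.** **Inputs (Section 9.2).** 12-month local control is 65% (SRS) and 80% (FSRT), with exponential TTLP. Loss of 50% by 12 months, mainly deaths, is also exponential. Follow-up is 12 months, one-sided alpha 2.5%, power 80%, with the Lachin-Foulkes method. Allocation is 1:1 (synopsis).

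**Hazards per year.** SRS: λ1 = −ln 0.65 = 0.4308. FSRT: λ2 = −ln 0.80 = 0.2231. Loss: η = ln 2 = 0.6931. HR = 0.2231/0.4308 = 0.518.

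**Probability of an observed event by 12 months**, P(λ) = λ/(λ+η) × [1 − exp(−(λ+η))]:
- SRS: 0.4308/1.1239 × (1 − 0.325) = 0.2587, or 191 × 0.2587 = 49.4 events
- FSRT: 0.2231/0.9163 × (1 − 0.400) = 0.1461, or 191 × 0.1461 = 27.9 events
- Total: 77.3

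**Reproducing 382.** With φ(λ) = λ²/P(λ) and λ̄ = 0.3270: φ(λ̄) = 0.5216, φ(λ1) = 0.7173, φ(λ2) = 0.3408.

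N = [1.960 × √(4φ(λ̄)) + 0.8416 × √(2φ(λ1) + 2φ(λ2))]² / (λ1 − λ2)² = [1.960 × 1.4445 + 0.8416 × 1.4547]² / 0.2076² = 381.5, which rounds to 382.

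The stated 82 events do not come out of the same inputs. Exponential loss gives 77.3, and loss spread uniformly over the year gives 80.3. This does not affect the point.

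**Sensitivity to selective exclusion (illustration).** FSRT exposure is 27.9/0.2231 = 125.1 patient-years. A progressor's mean time to event within the year is 1/0.9163 − 0.400/0.600 = 0.425 years. Removing three FSRT progressors leaves 24.9 events over 125.1 − 1.3 = 123.8 patient-years, a hazard of 0.201. The HR falls by the factor 0.201/0.2231 = 0.90, from 0.518 to about 0.467. Three patients are 0.8% of 382.

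**Headcount.** Power at N is Φ[(√N × 0.2076 − 1.960 × 1.4445)/1.4547]. Exclusion rates are not in the protocol, so those below are assumed. The first power column uses the stated 12-month follow-up. The second assumes 15 months with unchanged hazards.

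| Excluded | Analysed | Power, 12 months | Power, 15 months |
|---|---|---|---|
| 0% | 382 | 80.1% | |
| 5% | 363 | 78.0% | 82.6% |
| 10% | 344 | 75.8% | 80.6% |

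With 10% excluded, power would be 83.7% at 18 months and 87.2% at 24 months.

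**The case against.** **This belongs in the SAP.** What counts as major, who decides and when are details that a protocol may leave to the SAP, and their absence is not held against it here. That part of the objection stands. But Section 9.3 fixes the exclusion and the name of the set. An SAP could restore an all-randomized primary analysis only by contradicting the protocol.

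**The ICH E9 reference and blinded imaging review are safeguards.** The reference by itself sets no conditions on the exclusion in this protocol, and the blinded review concerns progression only.

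**The three-progressor example is one-sided.** It is. It assumes that all exclusions fall in one arm, are events and favour FSRT. Nothing in the protocol predicts that pattern, so it shows only how few patients matter.

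A reader might also infer four stronger things that the protocol does not support.

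- *Any exclusion takes the trial below 80% power.* This holds only if follow-up stops at 12 months. Section 9.2 deliberately leaves out the gain from follow-up of up to 24 months, and states the 50% loss as an upper limit.
- *Fewer than 80 events are planned.* The protocol plans 82. The 77 above is a recomputed 12-month expectation.
- *FSRT patients face more eligibility scrutiny because they attend 12 sessions.* Eligibility concerns baseline status, assessed at screening, and both arms share one follow-up schedule. This is speculation.
- *Ineligible patients vanish from every analysis.* The toxicity sentence can be read as keeping those who were treated. It conflicts with the case-report rule and needs reconciling.

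**Conclusion.** The point holds for the primary analysis population. As written, the confirmatory test compares what remains after eligibility exclusions in an open trial, under a label that does not fit, and no analysis of all randomized patients would reveal the effect. The bias cannot be sized from the protocol, because neither the number nor the pattern of exclusions is known. The roughly 10% shift in HR from three patients measures sensitivity, on the protocol's 12-month inputs, and is not a forecast.

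The sample size point is secondary. The 12-month calculation equates evaluable with total patients and so allows no headcount for exclusions. The cost is about 2 points of power at an assumed 5% and 4 points at an assumed 10%. Longer follow-up may well cover this if hazards persist, and the point disappears if all randomized patients are analysed.

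**What to change.** In Section 9.3:

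1. Define the primary analysis set as all randomized patients, analysed in the arm to which they were randomized, including those later found ineligible.
2. Move the exclusion for major eligibility violations to a sensitivity analysis, for example the per-protocol set. Fix the list of excluded patients blind to arm and outcome before database lock.
3. Reconcile the case-report rule with the toxicity-set sentence, so that it is clear whether treated ineligible patients count for safety.

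With these changes 382 randomized equals 382 analysed and needs no inflation. If the sponsor keeps the exclusion, the set should be renamed. Section 9.2 should then either enlarge the total (382/0.95 = 403 at an assumed 5%; 382/0.90 = 425 at an assumed 10%) or say that follow-up beyond 12 months is meant to cover exclusions.

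The cost of the recommended change is wording, plus slight dilution of the estimated effect by a few ineligible patients.
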